### **Neutropenia:**

If the absolute neutrophil count (ANC) decreases to less than  $1.0 \times 10^9/L$ , the study drug should be discontinued.

- If the ANC returns to above  $1.0 \times 10^9/L$ , the study drug may be restarted. When restarting the study drug, the dose should be reduced to 100 mg twice daily or matching placebo for the remainder of the study.
- In patients who restart fostamatinib at 100 mg BID after neutropenia resolves within the 14-day window, and labs are not rechecked during hospitalization, the team must either: 1) repeat CBC with differential within 7 days of discharge OR 2) not restart the medication if they are unable to repeat CBC with differential in this 7-day time frame.

- A CBC with differential will be checked daily while the patient is in the hospital and on study drug. If the patient is discharged with an ANC <  $1.0 \times 10^9/L$  then a repeat CBC with differential will be performed within 7 days of hospital discharge and repeated weekly for 4 weeks or until the ANC is  $>1.0 \times 10^9/L$ .
- If a patient is found to have an ANC  $<1.0 \times 10^9/L$  as part of routine care after hospital discharge while still in the follow-up period, then a CBC with differential should be checked weekly for 4 weeks or until the ANC is  $>1.0 \times 10^9/L$ .
- Study drug is not restarted when the ANC remains  $<1.0 \times 10^9/L$ . Those who are discharged with a normal ANC require no further measurement after discharge.

**Medication Interactions:**

Patients will be monitored after randomization to ensure the following medications are not started during study treatment: Atazanavir, Certinib, Clarithromycin, Cobicistat and cobicistat-containing coformulations, Idelalisib, Indinavir, Itraconazole, Ketoconazole, Levoketoconazole, Lonafarnib, Lopinavir, Mifepristone, Mibefradil, Nefazodone, Nelfinavir, Ombitasvir-paritaprevir-ritonavir plus dasabuvir, Posaconazole, Ribociclib, Ritonavir, Saquinavir, Telithromycin, Troleandomycin, Tucatinib, Voriconazole) from randomization to 21 days post-randomization. For a full list of CYP3A4 substrates, please reference this regularly updated list: <https://drug-interactions.medicine.iu.edu/MainTable.aspx>.

***22.8 Fostamatinib Arm Logistics***

The use of fostamatinib for the proposed indication is investigational and the study will be conducted under FDA IND #154000 and will cross reference IND #152131. Fostamatinib can be stored at room temperature, 20°C to 25°C (68°F to 77°F); excursions permitted between 0°C to 40°C (32°F to 104°F). Rigel has adequate investigational product and placebo to enroll 300 active and 300 placebo patients.

For regulatory reporting purposes, including identification and potential expedited reporting of 'SUSAR' events, the following serious and/or non-serious Adverse Events/Reactions are among the events that are considered expected for this study:

- Neutropenia
- Diarrhea
- Elevated AST, ALT, or bilirubin. However, AST or ALT greater than 10 times the local laboratory ULN or the baseline value at the time of randomization, whichever is greater, is considered unexpected for fostamatinib study drug for the purposes of adverse event reporting.
- Hypertension

The following is considered an AESI for the fostamatinib arm:

- AST or ALT greater than 5 times the local laboratory ULN or the baseline value at the time of randomization, whichever is greater

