- Adverse Events that are Serious OR are Definitely or Possibly Related (or of Uncertain Relationship) OR are a Grade 3 or 4 Clinical AE (isolated laboratory abnormalities that are not associated with signs or symptoms are not collected)

We outline the safety data collected in Table 2.

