**Generic AE Grading Scale**

Grade 1	Events causing no or minimal interference with usual social and functional activities, and NOT raising a concern, and NOT requiring a medical intervention/ therapy.
Grade 2	Events causing greater than minimal interference with usual social and functional activities; some assistance may be needed; no or minimal medical intervention/therapy required.
Grade 3	Events causing inability to perform usual social and functional activities; some assistance usually required; medical intervention/therapy required.
Grade 4	Events causing inability to perform basic self-care functions; medical or operative intervention indicated to prevent permanent impairment, persistent disability, or death.
Grade 5	Events resulting in death.

**An Adverse Event of Special Interest (AESI)** will be defined as a pre-specified event of scientific or medical concern that has the potential of being related to study drug and is important to understand regardless of investigator classifications. AESIs included below will be recorded in the adverse event eCRF and will require a written narrative.

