**PSESEs are exempt from adverse event reporting unless:**

1. the event is determined to be Serious and Definitely or Possibly Related to the study drug or study procedures;
2. the event is determined to be Unexpected and Definitely or Possibly Related to the study drug or study procedures; or

This approach is taken to avoid creating an overly cumbersome safety oversight environment by identifying expected clinical outcomes as safety events and obscuring real safety signals. Even as they are exempted from expedited reporting requirements, PSESEs will be reviewed regularly (unblinded, by treatment arm) by the DSMB to maintain the integrity of safety monitoring for the trial. PSESEs that meet none of the criteria above will not be recorded or reported as AEs.

PSESEs may occur during the initial hospitalization, lead to a re-admission, or occur in a later hospitalization during follow-up. The following are study-specific exempt serious events:

- Death (not Definitely or Possibly Related to the study drug or study procedures)
- Neurological Events:
  - Seizure

- Stroke
- Cardiovascular Events:
  - Hypotension as defined by low arterial blood pressure leading to either [1] initiation or increase in vasopressor therapy, [2] administration of a fluid bolus of 500 ml or more, or [3] modification of the dose or discontinuation of the study drug.
  - Atrial or ventricular arrhythmia
  - Cardiomyopathy
  - Cardiac arrest
  - Myocardial injury
  - Acute coronary syndrome
  - Hypertension as defined by elevated arterial blood pressure leading to either [1] initiation or increase in antihypertensive medications or [2] discontinuation of the study drug
- Respiratory events:
  - Hypoxemia requiring supplemental oxygen
  - Acute respiratory distress syndrome
  - Receipt of non-invasive or invasive mechanical ventilation
  - Receipt of extra-corporeal membrane oxygenation
- Gastrointestinal events:
  - Elevation in aspartate aminotransferase or alanine aminotransferase
  - Acute pancreatitis
- Renal events:
  - Acute kidney injury
  - Receipt of new renal replacement therapy
- Endocrine events:
  - Symptomatic hypoglycemia
- Hematologic or coagulation events:
  - Neutropenia, lymphopenia, anemia, or thrombocytopenia
  - Venous thromboembolism
- Dermatologic events:
  - Severe dermatologic reaction (e.g., Steven's Johnson Syndrome)

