### Hepatotoxicity:

**Inpatient monitoring:** Liver function tests (LFT's) will be checked daily during hospitalization while on study drug.

- 1) Study drug should be stopped if there is an increase in either:

- a. AST or ALT greater than or equal to 5-times the upper limit of normal at the local lab or for those with elevated AST and ALT at the time of enrollment an increase to 5-times the level at enrollment
- b. AST or ALT to greater than or equal to 3-times the upper limit of normal at the local lab AND total bilirubin to greater than or equal to 2-times the upper limit of normal at the local lab.

Elevated unconjugated (indirect) bilirubin in absence of other LFT abnormalities – continue study drug with frequent monitoring since isolated increase in unconjugated (indirect) bilirubin may be due to UGT1A1 inhibition.

**Outpatient monitoring:** Patients discharged while on study drug with AST/ALT or bilirubin elevated > 2x the upper reference limits or up trending from most recent value (but less than the inpatient stopping criteria) AND patients discharged not on study drug with either AST or ALT at least 3-times the upper limit of normal or total bilirubin at least 2-times the upper limit of normal at the time of discharge will have the following study procedures performed:

1) 7 (+/-2) days post-hospital discharge a repeat measurement of AST, ALT and total bilirubin will be obtained.

- a. Patients NOT on study drug at the time of repeat LFT measurement:

\*If these repeat measurements are less than 3-times the upper limit of normal for AST or ALT and less than 2-times the upper limit of normal for total bilirubin, then no further study procedures will be performed related to LFT monitoring.

\*If these repeat measurements are greater than 3-times the upper limit of normal for AST or ALT or greater than 2-times the upper limit of normal for total bilirubin, then a repeat measurement of AST, ALT and total bilirubin should be obtained 7 (+/-2) days later. If the AST or ALT remain above 3-times the upper limit of normal or total bilirubin is above 2-times the upper limit of normal after this repeat testing 7 days later, LFTs should be monitored per standard of care by a provider or if no provider followed-up by the study team.

[figure not shown]
- b. Patients ON study drug at the time of repeat LFT measurement:

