\*If these repeat LFT measurements are below the upper reference limit of normal continue study drug to completion and no recheck is needed.

\*If these measurements remain above the upper reference limit of normal for either AST, ALT or total bilirubin but do not meet inpatient stopping criteria (defined above), continue study drug and a repeat measurement of AST, ALT and total bilirubin should be obtained 7 (+/-2) days later. If this repeat testing remains above the upper limit of normal for AST, ALT or bilirubin it should be monitored per standard care by a provider or if no provider followed-up by the study team.

\*If study drug is stopped (per inpatient stopping rules above) repeat measurement of AST, ALT and total bilirubin should be obtained 7 (+/-2) days later. If this repeat testing remains above the upper limit of normal for AST, ALT or bilirubin it should be monitored per standard care by a provider or if no provider followed-up by the study team.

Once study drug is stopped for abnormal LFT values, the study drug will not be restarted.

\*up trending is defined as a >25% increase in LFTs from the day prior

**Diarrhea:** If symptoms become severe (grade 3 or above) while the patient is hospitalized, temporarily stop study drug until symptoms resolve to mild (grade 1). When restarting, study drug dose should be reduced to 100 mg twice daily or matching placebo for the remainder of the study. Study drug should be stopped if diarrhea becomes severe in the outpatient setting.

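### A permanent fostamatinib stop for combined AST/ALT and bilirubin elevation, with enzymes at or below the liver AESI cut-off, triggers no mandatory adverse event record or narrative

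*Protocol*

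**What the plan says.** - **Stopping.** Protocol 22.7 (Hepatotoxicity) has two alternative inpatient liver limbs. Limb (a) is AST or ALT at or above 5 times ULN, or 5 times the enrolment level for patients who entered with raised values. Limb (b) is "AST or ALT to greater than or equal to 3-times the upper limit of normal at the local lab AND total bilirubin" at or above 2 times ULN. Either stop is permanent: "Once study drug is stopped for abnormal LFT values, the study drug will not be restarted".
- **Exclusion.** The limb (b) combination is also an arm-specific exclusion criterion in 22.6. Section 22.5 lists elevated liver tests among the labelled warnings.
- **AESI.** The single AESI in 22.8 is "AST or ALT greater than 5 times the local laboratory ULN or the baseline value at the time of randomization, whichever is greater". It has no bilirubin component. Under 13.1, "AESIs included below will be recorded in the adverse event eCRF and will require a written narrative".
- **Exempt events.** The list of protocol-specified exempt serious events (PSESEs) in 13.2 contains "Elevation in aspartate aminotransferase or alanine aminotransferase", with no threshold, grade or bilirubin. The default is that "PSESEs that meet none of the criteria above will not be recorded or reported as AEs".
- **Expectedness.** Section 22.8 treats raised AST, ALT or bilirubin as expected. Only AST/ALT above a 10-times limit is unexpected; bilirubin has no upper limit.
- **AE collection.** Section 13 adds to its list of collected AEs that "isolated laboratory abnormalities that are not associated with signs or symptoms are not collected".
- **SAP.** Section 3.3 has no hepatic row. A liver PSESE falls under the general row for other PSESEs.

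**The concern.** The protocol regards the combined pattern as sufficient to keep a patient out of the arm and to end study drug for good. AESI status is the device that guarantees an AE entry and a narrative whatever the investigator's classification, and here it is tied to the enzyme value alone. A report could state the number of hepatic AESIs and leave out patients whose drug was stopped under limb (b) with lower enzymes. Whether those patients have any AE record would then rest largely on individual judgements at the sites.

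**Working it through.** The plan states no figure to reproduce. The check compares thresholds and then follows the recording routes.

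**1. The band.** Express AST/ALT (e), bilirubin and baseline enzyme (b) in multiples of ULN. Limb (b) requires e ≥ 3 and bilirubin ≥ 2. The AESI wording can be read in two ways:

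- Reading 1: e > 5 × max(1, b)
- Reading 2: e > max(5, b)

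A limb (b) stop that is not an AESI has e from 3 up to the cut-off, inclusive. Section 22.6 keeps b below 5.

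| Baseline b | Reading 1 cut-off | Gap, reading 1 | Reading 2 cut-off | Gap, reading 2 |
|---|---|---|---|---|
| ≤ 1 | 5 × 1 = 5 | 3 to 5 | 5 | 3 to 5 |
| 2 | 5 × 2 = 10 | 3 to 10 | 5 | 3 to 5 |
| 3 | 5 × 3 = 15 | 3 to 15 | 5 | 3 to 5 |
| 4.9 | 5 × 4.9 = 24.5 | 3 to 24.5 | 5 | 3 to 5 |

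Under reading 2 the baseline term never binds for an eligible patient, because b < 5. That favours reading 1 as the intention, but the text does not say so.

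**2. Example patients.**

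- e = 4, bilirubin 3, b = 1: limb (b) stop; not an AESI and not unexpected under either reading.
- e = 5.1, bilirubin 2, b = 1: limb (b) stop; AESI under both readings.
- e = 8, bilirubin 3, b = 2: limb (b) stop; not an AESI under reading 1 (8 ≤ 10), AESI under reading 2 (8 > 5).

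**3. Routes to an AE record inside the band.**

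- *AESI:* closed, by step 1.
- *Unexpected and related PSESE:* closed. If both limits in 22.8 are read the same way, the 10-times limit lies above the AESI cut-off for every eligible baseline, and raised bilirubin is expected without limit.
- *Grade 3 or 4 clinical AE:* closed if the event is a PSESE, because 13.3 and 13.4.2 confine this route to events that are not PSESEs.
- *Serious and related PSESE:* open. The 13.2 exception applies where "the event is determined to be Serious and Definitely or Possibly Related to the study drug or study procedures"; 13.3 also admits an uncertain relationship. Both seriousness and relatedness are investigator judgements, and 13.1 allows seriousness on medical judgement.
- *Non-PSESE event:* unclear. Bilirubin is not on the PSESE list, so a site could record that component, or a liver diagnosis under 13.1, as an ordinary AE. The section 13 exclusion of isolated laboratory abnormalities pulls the other way. The documents do not say whether an enzyme-plus-bilirubin rise that stopped drug counts as isolated.
- *Stop reason (7.7.3):* captured, but a possible AE or PSESE only sends the site back to the same two pages.

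**4. Count.** The documents give no rate. If 1% to 3% of 300 active patients fell in the band (an assumption), that would be 300 × 0.01 = 3 to 300 × 0.03 = 9 cases without a required narrative.

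**The case against.** Nothing obliges an AESI to mirror a stopping rule. Neutropenia, hypertension and severe diarrhea also interrupt or stop drug under 22.7, and none is an AESI. This is fair: the plan breaks no rule of its own. But a liver AESI does exist, and it tracks the enzyme-only limb while leaving out the combined one, so the mismatch lies within a single organ's rules.

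Two stronger readings are tempting, and the documents do not support either.

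- *A reader might infer that such a patient is reported only as an ungraded enzyme elevation.* A case above the AESI cut-off is an AESI. A case judged serious and related is also an AE and is graded under 13.1. Because 13.2 records any event that is not a PSESE as an AE, the missing bilirubin item may open a route instead of closing one. Whether the PSESE form captures values or grade is not shown.
- *A reader might infer that there is no count by arm and that the DSMB would not see these patients.* Section 13.2 has the DSMB review PSESEs unblinded by arm, and SAP 7.2 reports PSESE frequencies and drug stoppages to it. What is missing is a specified count of the limb (b) pattern.

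A further objection stands in full. A limb (b) row against the pooled placebo group would compare unequal ascertainment. Daily liver tests are mandated only in the fostamatinib arm, in hospital, on study drug (7.7.1; Table 1, footnote 5), whereas SAP 2.2 pools every placebo patient eligible for the arm, whichever arm they entered.

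**Conclusion.** The point holds for a defined band. A limb (b) stop at or below the AESI cut-off has no guaranteed AE entry or narrative, and the likely default is a PSESE item that does not identify the pattern. For baseline enzymes at or below ULN the band is 3 to 5 times ULN, and this needs no assumption. The wider band for raised baseline depends on reading 1. The number of patients is unknown; 3 to 9 is illustrative only.

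This is a gap in safety reporting. It leaves the primary analysis untouched and is no evidence that the stopping rules are wrong. It is worth correcting because the protocol acts on this liver pattern twice, by exclusion and by permanent stop, without requiring that it be documented systematically.

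**What to change.** 1. Reconcile Protocol 13.2, 22.7 and 22.8. Add the existing limb (b) wording to the fostamatinib AESI definition for reporting purposes, so that meeting it requires an AE record and a narrative.
2. State in 22.8 which reading of the whichever-is-greater clause applies. The same clause governs the 10-times limit for unexpected events, so settle both together.
3. If SAP 3.3 tabulates limb (b) cases, derive them from the recorded AST, ALT and total bilirubin values. Compare active with placebo among participants assigned to the fostamatinib arm, over inpatient days on study drug, and do not use the pooled placebo group. Under SAP 2.3 each stratum with m eligible arms allocates m active to 1 placebo within an arm, so show each group's own denominator and take the eligibility stratum into account.

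No dose, stopping rule or clinical threshold changes. The cost is wording in two documents, probably a few extra narratives and, if step 3 is adopted, one derived variable. The within-arm placebo group may be smaller than the pooled one, so that comparison should be descriptive.

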## 23 Appendix E. Non-NAT Tests Deemed with Equivalent Specificity to NAT by the Protocol Team

Date EUA* Updated (first issued)	Manufacturer	Diagnostic (Letter of Authorization)	PPA- Sensitivity	NPA- Specificity	Antigen	Days since symptom onset
13-Jan-2021 (02-Jul-2020)	Becton, Dickinson and Company (BD)	BD Veritor System for Rapid Detection of SARS-CoV-2	84%	100%	nucleocapsid	5
(11-Jan-2021) 11-Jan-2021	Ortho Clinical Diagnostics Inc.	VITROS Immunodiagnostic Products SARS-CoV-2 Antigen Reagent Pack	90.0% (76.3–97.2%)	100% (95% CI: 99.1–100.0%)	nucleocapsid	7
01-May-2021 (01-May-2021)	Quanterix Corporation	Simoa SARS-CoV-2 N Protein Antigen Test	97.7 % (95% CI: 92.03-99.72)	100% (95% CI: 90.75-100.0)	nucleocapsid	14
23-Dec-2020 (15-Dec-2020)	Ellume Limited	Ellume COVID-19 Home Test	95% [95% CI 82% - 99%]	97% [95% CI 93% - 99%]	nucleocapsid	w/ or wo/ symptoms
22-Dec-2020 (18-Dec-2020)	Quidel Corporation	QuickVue SARS Antigen Test	96.6%	99.3%	nucleocapsid	5
16-Dec-2020 (26-Aug-2020)	Abbott Diagnostics Scarborough, Inc.	BinaxNOW COVID-19 Ag Card	84.6% (95% CI: 76.8% - 90.6%)	98.5% (95% CI: 96.6% - 99.5%)	nucleocapsid	7
16-Dec-2020 (16-Dec-2020)	Abbott Diagnostics Scarborough, Inc.	BinaxNOW COVID-19 Ag Card Home Test	91.7% (95% CI: 73.0% - 98.9%)	100.0% (95% CI: 87.7% - 100.0%)	nucleocapsid	7
07-Dec-2020 07-Dec-2020	Luminostics, Inc.	Clip COVID Rapid Antigen Test	96.9% (95% CI: 83.8% - 99.9%)	100% (95% CI: 97.3% - 100%)	nucleocapsid	7
23-Oct-2020 (23-Oct-2020)	Celltrion USA, Inc.	Sampinute COVID-19 Antigen MIA	99.4 %	100%	receptor binding domains (RBDs) spike proteins	5
13-Oct-2020 (08-Oct-2020)	Access Bio, Inc.	CareStart COVID-19 Antigen test	88.4 %	100%	nucleocapsid	5
02-Oct-2020 (02-Oct-2020)	Quidel Corporation	Sofia 2 Flu + SARS Antigen FIA	95.2 %	100%	nucleocapsid	5
18-Aug-2020 (18-Aug-2020)	LumiraDx UK Ltd.	LumiraDx SARS-CoV-2 Ag Test	97.6 % (91.6 % - 99.3 %)	96.6 % (92.7 % - 98.4 %)	nucleocapsid	12
17Jul 2020 (08-May-2020)	Quidel Corporation	Sofia SARS Antigen FIA	96.7 % (96.7% - 99.4 %)	100 % (97.9% - 100.0 %)	nucleocapsid	-

CTCAE	Common Terminology Criteria for Adverse Events
DAG	Data Access Group
DAIDS	Division of Acquired Immunodeficiency Syndrome
DCC	Data Coordinating Center
DOB	Date of Birth
DOR	Delegation of Responsibilities
DR	Disaster Recovery
DSMB	Data Safety Monitoring Board
DSMP	Data Safety Monitoring Plan
eConsent	Electronic Consent
eCRF	Electronic Case Report Forms
EDC	Electronic Data Capture
EMR	Electronic Medical Record
FAQ	Frequently Asked Question
FDA	Food and Drug Administration
GDPR	General Data Protection Regulation
GUID	Globally Unique Identifier
HT	Host Tissue
hsTn	High-sensitivity Troponins
ICF	Informed Consent Form
ICH GCP	International Conference of Harmonization Good Clinical Practice
ID	Identity
IMV	Invasive Mechanical Ventilation
INR	International Normalized Ratio
IP	Investigational Product

IRB	Institutional Review Board
IT	Information Technology
ITT	Intent-To-Treat
KSP	Key Study Personnel
LAR	Legally Authorized Representative
LFT	Liver Function Test
MOP	Manual of Procedures
NAT	Nucleic Acid Test
NHLBI	National Heart, Lung, and Blood Institute
NINDS	National Institute of Neurological Disorders and Stroke
NTproBNP	N-terminal prohormone B-type natriuretic peptide
N3C	National COVID Cohort Collaborative
PDF	Portable Data Format
PI	Principal Investigator
PSESE	Protocol-Specified Exempt Serious Events
PT	Prothrombin Time
PTT	Partial Thromboplastin Time
REDCap	Research Electronic Data Capture
RTI	Research Triangle Institute
SAP	Statistical Analysis Plan
SAE	Serious Adverse Event
SIRB	Single Institutional Review Board
SOC	Standard of Care
SOFA	Sequential Organ Failure Assessment
UAT	User Acceptance Testing
VCC	Vanderbilt Coordinating Center
VMP	Validation Master Plan
VUMC	Vanderbilt University Medical Center
VUMC-IT	Vanderbilt University Medical Center – Information Technology
VICTR-ORI	Vanderbilt Institute for Clinical and Translational Research – Office of Research Informatics
WHO	World Health Organization

1 INTRODUCTION

The Statistical Analysis Plan (SAP) was developed by DCC statisticians in collaboration with study team leadership and NHLBI representatives. The SAP describes treatment arms, analysis datasets, all outcomes and planned analyses, randomization procedure and algorithm, decision thresholds and interim stopping rules, design and results of simulations to determine power and sample size and demonstrate study operating characteristics, procedures for handling missing data, and any other information that is essential to carry out all statistical analyses.

